## 10.11. Role of Sponsors Representatives

Sponsor's representatives may provide support as required for the clinical study, including technical support or training staff in the different hospital units. The sponsor will collaborate with investigator to implement the SM strategy which may include a sponsor implementation team to assist the site with adopting the SM strategy into their clinical workflow.

# 11. Risks and Benefits

## 11.1. Potential Risks

Risks under this protocol relate to both study devices and study procedures. The devices in this study are non-invasive, post-market products with FDA clearance, and will be used in accordance with their labeling. The clinical protocol design is minimal risk to the subject.

Following is a list detailing potential risks from the Vital Sync™ IM & VPMP, the BioModule, and the clinical study protocol.

### Risk associated with the Vital Sync™ IM & VPMP

- Use errors could cause delay in treatment or incorrect treatment. Potential use errors include manually entering incorrect parameter values, adjusting the alarm priority for the incorrect alarm, or an unauthorized user disassociating devices from patients. Multiple design mitigations such as

This document is electronically controlled. Printed copies are considered uncontrolled.

**Confidential**

Protocol #: COVMOPO0561

Rev E 09AUG2017

data validation, administrator account, and user interface acknowledgement messages have been implemented to reduce the possibility of hazardous situations arising from use errors.

- Use of the Vital Sync™ IM & VPMP by clinicians remotely viewing patient data in a non-secure environment presents potential risk of breaches of patient confidential data from clinicians remotely viewing patient data. Mitigations for patient privacy risks include security on the software server architecture, providing instructions for users on how to lock down the bedside displays' operating system, and instructing users to utilize a secure network for remote viewing of patient data.
- Environmental risks could cause delay in treatment. Potential environmental risks includes radio interference, patient being out of range, and network failure. This would result in delay in treatment since the patient would experience a loss of monitoring, sending stale data over the network, or having the clinician unable to receive the alert notification. Environmental risk mitigations include an aged data indicator, message time stamps, disconnect and performance notifications.

[REDACTED]

**Risks associated with clinical study protocol:**

There are no known risks associated specifically with the clinical study protocol.

This document is electronically controlled. Printed copies are considered uncontrolled.

**Confidential**

Protocol #: COVMOPO0561

Rev E 09AUG2017

Inclusion and exclusion criteria have been described to recruit only appropriate subjects into the study. Potential subjects who may be at increased risk from the devices will not be enrolled. For example, subjects with implanted pacemaker or defibrillator will not be included. If there is any question of the subject meeting inclusion/exclusion for enrollment, Medtronic should be contacted to discuss first.

## 11.2. Potential Benefits

Subjects' participation in this study may offer no additional benefit in respect to the same monitoring provided outside of the study.

Possible benefits for participating in this study include the following (although others are possible):

- Subjects in SM arm may benefit from the alternative surveillance monitoring strategy via detection of clinical deterioration during the course of hospital stay.

There is, however, the potential for benefiting future patients should this study lead to the development of safer, more accurate, more cost-effective, and easier-to-use medical monitoring devices.

Since this is not a treatment study, the alternative is to not participate in the study.

## 11.3. Risk-Benefit Rationale

Medtronic believes that the potential risks associated with the conduct of this trial are minimal using nonsignificant risk, non-invasive study devices for the following reasons:

- All the devices used in the study are cleared by FDA and available in the hospitals and used within their intended use.
- Surveillance monitoring will be performed in addition to standard patient "spot-check" monitoring performed by hospital staff.
- The "Instructions for Use" and product labeling for the devices which will be provided to investigator prominently include statements that clearly advise users about how to properly use the system and interpret the output. Thus, users will clearly be instructed how to avoid and prevent many of these risks.
- The expected likelihood that any of these failure modes could occur during conceivable use of the BioModule on a patient is very small. The likelihood that an actual injury would occur if a rare failure mode of the BioModule occurs simultaneously is vanishingly small. This analysis is based upon clinical experience as well as a wide body of published knowledge on the magnitude and impact of changes in physiology of low acuity patients possibly monitored with the BioModule.
- Risk of injury is further mitigated because routine clinical observation is frequently deployed in addition to any monitoring. Based on the results of the risk benefit analysis, the benefits outweigh the risks for basic physiologic monitoring.

## 12. Adverse Event Assessments

Only the following adverse events will be collected for this study:

This document is electronically controlled. Printed copies are considered uncontrolled.

**Confidential**

Protocol #: COVMOPO0561

Rev E 09AUG2017

- Any adverse events noting mild or moderate physiological deterioration
- Any adverse event whose relationship to the study device is: possible, probable, definite, or unknown/ impossible to determine, regardless of what the event may be.
- All SAEs, of any relationship, meeting definition in section 12.2 of the CIP must be reported.

The recording of adverse events for all enrolled subjects begin after the study devices are attached and ends with the subject's completes study enrollment. Completion is defined by when a subject is discharged from the hospital, completes 30 day ( $\pm$  2 days) enrollment period, or if the subject is withdrawn from the study for any reason.

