### 12.2. Definitions/Classifications

For the purposes of the clinical report, the sponsor will classify each adverse.

- **Adverse Events (AE):** Any untoward medical occurrence, unintended disease or injury, or untoward clinical signs (including abnormal laboratory findings) in subjects, users or other persons, whether or not related to the medical device.

NOTE 1: This definition includes events related to the investigational medical device or the comparator.

NOTE 2: This definition includes events related to the procedures involved.

NOTE 3: For users or other persons, this definition is restricted to events related to investigational medical devices.

- **Adverse Device Effect (ADE):** Adverse event related to the use of a medical device.
  - NOTE 1: This definition includes adverse events resulting from insufficient or inadequate instructions for use, deployment, implantation, installation, or operation, or any malfunction of the investigational medical device.
  - NOTE 2: This definition includes any event resulting from use error or from intentional misuse of the investigational medical device
- **Serious Adverse Event (SAE):** Adverse event that
  1. led to death,
  2. led to serious deterioration in the health of the subject, that either resulted in
    - a. a life-threatening illness or injury, or
    - b. a permanent impairment of a body structure or a body function, or
    - c. in-patient or prolonged hospitalization, or
    - d. medical or surgical intervention to prevent life-threatening illness or injury or permanent impairment to a body structure or a body function,
  3. led to fetal distress, fetal death or a congenital abnormality or birth defect

This document is electronically controlled. Printed copies are considered uncontrolled.

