### 12.3. Recording and Reporting Adverse Events and Device Deficiencies

Adverse Event and Device Deficiency information will be collected throughout the study on the source, eCRF, AE log, or the Device Deficiency form located in the Investigator Site File (ISF).

Information reported on the CRF will include:

- Adverse Event diagnosis term to be determined by investigator
- A detailed description of the event
- The date of event onset
- The relatedness of the event to the device to be determined by investigator
- The relatedness of the event to the procedure to be determined by investigator
- Severity to be determined by investigator
- Actions taken as a result of the event per investigator
- The outcome of the event
- The date the event was first noticed by the investigator
- For device deficiency, determine if it could have led to a SADE

The investigator must report any SADE/SAE to the sponsor and IRB as soon as possible, but no later than 10 working days after the investigator learns of the effect.

Medtronic will conduct an evaluation of any SADE/SAE after first receiving notice of the event and report the results to all reviewing IRBs, the participating investigator and, if the effect is determined to be device-related, to the FDA.

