**Confidential**

## 7.2. General Methodology

In general, descriptive statistics will be used to summarize baseline and study outcomes. For continuous variables, number of available observations, mean, standard deviation, median, minimum and maximum values will be provided. For categorical variables, frequency and percentage will be used. Unless otherwise specified, statistical assessments will be based on 2-sided tests at an alpha level of 0.05, which include Student-t or Wilcoxon rank-sum or ANOVA test for continuous variables, and Chi-square or Fisher's exact test for categorical variables. Multivariate regression models will be used to assess impacts of potential confounding variable. Statistical analysis will be performed using [REDACTED] (SAS Institute Inc., Cary, NC) or other valid statistical software.

The primary effectiveness analysis will be based on all evaluable data from this study. A per protocol analysis will be performed based on all subjects who are compliant with the study protocol, i.e. who provide valid informed consents and do not experience any major protocol deviations.

For safety assessments, adverse events (AEs) will be summarized using frequency counts and percentages. Descriptive statistics will be provided by monitoring group and by severity and relationship. Additionally, differences between the two monitoring groups will be summarized along with 95% confidence intervals. Individual listings of adverse events, including event type, start date, duration, severity, and device-relatedness will be provided as appropriate. The safety analysis will be based on all patients participated in the study.

Further, a health economic analysis will be performed based on healthcare economic and resource utilization data collected in this study. Monitoring effectiveness, QoL in the form of Quality-Adjusted Life-Years (QALYs), life-years gained and other data collected in this study may be used as inputs to the model.

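### The closed adverse-event list names mild and moderate deterioration but not severe, so a severe, non-serious deterioration judged unrelated to the device is not recorded and the severe row of the AE table is incomplete

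*Protocol*

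**What the plan says.** Protocol section 12 opens the collection rule with "Only the following adverse events will be collected for this study". Three items follow:

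1. "Any adverse events noting mild or moderate physiological deterioration"
2. "Any adverse event whose relationship to the study device is: possible, probable, definite, or unknown/ impossible to determine, regardless of what the event may be"
3. "All SAEs, of any relationship, meeting definition in section 12.2 of the CIP must be reported"

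SAP 7.10 carries the same list. The synopsis safety row is shorter: it mentions SAEs and device-related events, points to section 12, and has no deterioration item.

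Severity is a separate field on the case report form. Protocol 12.3 has "Severity to be determined by investigator" and gives no grading scale in the text available.

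On analysis, SAP 7.2 states "Descriptive statistics will be provided by monitoring group and by severity and relationship", and Protocol 13.3 says the same. Both add that group differences will be shown with 95% confidence intervals.

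**The concern.** Severity and seriousness are different scales. The first item of the list is limited by severity and stops at moderate. The third is limited by seriousness. Nothing in the list joins the two, so an event can be severe without being serious and fall between them unless the device item catches it. The result is an inversion: a mild, unrelated deterioration is recorded, while a severe, unrelated one that resolves without an SAE consequence is not.

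The trial places patients for whom telemetry was ordered on a different form of monitoring, so deterioration is the kind of adverse event a reader will look at first. If the severe row of the table is collected under a narrower rule than the mild and moderate rows, its counts and group difference do not mean the same thing as those beside them.

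**Working it through.** No stated figure in the plan bears on this point, so the check is logical: apply the three items to every kind of deterioration event and see what is left.

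**Inputs**

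- Collection rules: the three items of Protocol 12, the same in SAP 7.10.
- Seriousness: Protocol 12.2. An SAE needs death, a fetal or congenital outcome, or a serious deterioration with a listed consequence. Two of those consequences matter most for an inpatient: "in-patient or prolonged hospitalization, or" and "medical or surgical intervention to prevent life-threatening illness or injury or permanent impairment to a body structure or a body function".
- Severity: mild, moderate, severe. This three-level scale is an assumption, because the documents define none.
- Device relationship: judged unrelated, or any of possible, probable, definite and unknown.

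**Number of kinds of event:** 3 severities × 2 seriousness levels × 2 relationship levels = 12.

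| Severity | Serious? | Device relationship | Collected under |
|---|---|---|---|
| Mild or moderate (2 levels) | either | either | item 1: 2 × 2 × 2 = 8 kinds |
| Severe | yes | either | item 3: 2 kinds |
| Severe | no | possible, probable, definite or unknown | item 2: 1 kind |
| Severe | no | unrelated | none: 1 kind |

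Collected: 8 + 2 + 1 = 11 of 12. Not collected: 12 − 11 = 1. Within the severe row, 3 of 4 kinds are collected; within each of the mild and moderate rows, 4 of 4. These are counts of categories, not of events.

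**Does another section restore the missing kind?**

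- Protocol 10.2.2 (daily inpatient review) assesses events as section 12 provides, so it does not widen the list.
- The synopsis is narrower than section 12.
- Protocol 6.2.2 and 6.2.3 define unplanned ICU transfer, rapid response activation, code blue and unplanned intubation as endpoints. They capture deterioration that leads to one of those responses, but they are not adverse-event records with severity and relationship, and do not fill the table.
- SAP 7.2 and Protocol 13.3 describe how collected events are tabulated. They add none.

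**Effect on the table:** the mild and moderate rows hold all deterioration of that grade. The severe row holds only deterioration that is also serious or not judged unrelated to the device. The rows therefore rest on different inclusion rules.

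**The case against.** The best defence is that little is lost. Deaths, life-threatening events, permanent impairment, prolonged stays and interventions to prevent these are all SAEs and are collected whatever their relationship. Any event that might be related to the device, or whose relationship is unknown, is collected at any severity. To be missed by the trial altogether, a deterioration would have to be severe, meet no SAE criterion, be judged unrelated, and prompt no rapid response, code, intubation or ICU transfer. The drafters may also have intended mild or moderate deterioration to sit next to the serious deterioration of the SAE definition, so that the two together covered everything.

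The first part stands and limits the size of the point. The second does not close the gap: the documents never equate severe with serious, and the SAE definition requires a listed consequence, not a grade.

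Stronger readings are tempting, and the text does not bear them out:

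- A reader might infer that severe non-serious deterioration is never recorded. It is, when the device relationship is possible, probable, definite or unknown.
- A reader might infer that the table loses its severe end. It does not; severe SAEs and severe possibly related events are in it. The row is incomplete, not absent.
- A reader might infer that an event recorded as moderate is removed if it worsens to severe. Nothing in Protocol 12 or SAP 7.10 says so, and such an event had already qualified under the first item.
- A reader might infer a bias between groups, because the device item has an obvious application only where the study device is worn. That is possible, but the documents do not say how relationship is rated in telemetry subjects, so neither its presence nor its size can be shown.

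**Conclusion.** The list is wrong as written, in one narrow respect. On a literal reading, severe deterioration that is non-serious and judged unrelated to the study device is outside adverse-event collection in both documents, although milder deterioration of the same kind is inside it. The severe row of the planned table is incomplete and not comparable with the mild and moderate rows.

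The size cannot be given as a number of subjects. The documents state no event rate, and it would be a mistake to apply an assumed rate to the 132 per group in the sample-size sections: that figure is for the power of the length-of-stay comparison, whereas SAP 7.1.3 bases safety on everyone who took part. The gap is probably small, because most severe inpatient deterioration can be expected to meet an SAE criterion or to appear as one of the clinical endpoints; that is a judgement, not a figure from the plan. The primary analysis, sample size, power and alpha are unaffected.

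The conclusion assumes that the word restricting the list to the named items is meant literally and that severe is a grade above moderate on whatever scale the investigator uses.

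**What to change.** In Protocol 12 and SAP 7.10, reword the first item to: *Any adverse event noting physiological deterioration of any severity (mild, moderate or severe).* With that wording, whether an event is collected no longer depends on where an investigator draws the line between moderate and severe.

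Align the synopsis safety statement, which names only SAEs and device-related events, with the amended list.

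The cost is a text amendment to the two documents, handled under the amendment procedure in Protocol 15.7, and a few more adverse-event records.

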Respiration Rate	RR	A unit of measure that indicates rate of breathing in breaths per minute.
Serious Adverse Event	SAE	
Adverse event that
 
 
1. led to death,
 
2. led to serious deterioration in the health of the subject, that either resulted in 
 
a. a life-threatening illness or injury, or
 
b. a permanent impairment of a body structure or a body function, or
 
c. in-patient or prolonged hospitalization, or
 
d. medical or surgical intervention to prevent life-threatening illness or injury or permanent impairment to a body structure or a body function,
 
 
 
3. led to fetal distress, fetal death or a congenital abnormality or birth defect
 
 
Note: Planned hospitalization for a pre-existing condition, or a procedure required by the protocol, without serious deterioration in health, is not considered a serious adverse event.

Serious Adverse Device Effect	SADE	Adverse device effect that has resulted in any of the consequences characteristic of a serious adverse event.
Surveillance Monitoring	SM	The SM group will serve as the group who will be monitored by the study device for the duration of study enrollment on a medical-surgical unit(s).
Standard Operating Procedures	SOP	Medtronic Quality Standard Operating Procedures
Telemetry Monitoring	TM	The TM group will serve as the control group in this study and will be monitored via the site's standard of care telemetry practice/protocol.
Vital Sync™ Informatics Manager & Virtual Patient Monitoring Platform	Vital Sync™ IM & VPMP	A software only device that provides mobile and centralized remote monitoring.
Virtual Patient Monitoring Platform	VPMP	A display system that provides visual and audible renderings of physiologic data, waveforms, alarms and alerts routed through the Vital Sync™ IM from supported devices. The Vital Sync™

This document is electronically controlled. Printed copies are considered uncontrolled.

Term	Abbreviation	Definition
		VPMP displays information received from the IM on any web-enabled device.

This document is electronically controlled. Printed copies are considered uncontrolled.

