Study Procedures and Assessments	
Subjects who meet all of the inclusion criteria and none of the exclusion criteria will be assigned to either one of the monitoring groups and then followed for the duration of their hospital stay.
 
The monitoring groups will be enrolled in two prospective phases: telemetry monitoring (TM) OR surveillance monitoring. Enrollment of the TM group will occur first. After TM enrollment is complete, the enrollment phase of SM will initiate.
 
The TM group will serve as the control group and will be monitored via the site's standard of care telemetry practice/protocol. Subjects will continue to be enrolled in the study if subjects are transferred to medical-surgical unit after initial period of TM. No additional monitoring will be used for duration of study enrollment.
 
The SM group will undergo placement of the study device following study enrollment and hospital staff will implement the SM strategy for the duration of study enrollment. A dedicated medical-surgical unit(s) will be utilized for the SM phase.
 
Study procedures during the hospital stay will involve assessing eligibility, collecting baseline information, documenting clinical data from the eMR, unit transfers, discharges, and evaluating changes in health status.
 
All study related subject data will be documented and entered into the subjects' eCRF. All treatment will be standard of care per institutional practice.

Safety Assessments	Subjects will be monitored for Serious Adverse Events and Device-Related Adverse Events as noted in Section 12.
Statistics	Baseline and study outcomes will be summarized using descriptive statistics. One-way analysis of variance will be used to compare continuous variables (e.g., age, length of study) and Chi-square or Fisher's exact test will be used for categorical variables. Multivariate regression will be used to assess impacts of potential confounders. A P-value <0.05 is considered statistically significant unless otherwise specified.

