## 8.4. Product Use

The Vital Sync™ IM & VPMP will be used to allow clinicians to remotely view patient information collected from the BioModule and enable clinicians to be notified of clinical distress via color coded alarms and audible alerts. The BioModule will be attached to each subject and placed on the lower section of the sternum via two electrodes.

User guides and instructions for use of the Vital Sync™ IM & VPMP and BioModule™ will be provided to the study team prior to or at the Site Initiation Visit.

This document is electronically controlled. Printed copies are considered uncontrolled.

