**Clinical Team Satisfaction Questionnaire**

Eligible clinicians will be any clinician who provides inpatient care to the study subject participating during the SM phase of the study and interacts with the study devices, the Vital Sync™ IM & VPMP and the BioModule. The satisfaction questionnaire should be administered to clinicians at the end of the SM phase after all subjects have completed study participation.

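### Non-serious device reactions are collected by relation to the surveillance system only, so a between-group AE difference that includes them partly reflects the collection rule (minor)

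*Protocol*

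**What the plan says.** Protocol 12 opens with a closed list: "Only the following adverse events will be collected for this study". SAP 7.10 repeats it. There are three categories:

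1. AEs of mild or moderate physiological deterioration, whatever their cause.
2. "Any adverse event whose relationship to the study device is: possible, probable, definite", or of unknown or undeterminable relation.
3. All SAEs, of any relation.

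The Protocol uses the term study device for the SM system:

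- Glossary: "The SM group will serve as the group who will be monitored by the study device for the duration of study enrollment".
- Synopsis, study procedures: "The SM group will undergo placement of the study device following study enrollment".
- Section 10.2.4, on clinicians eligible for the satisfaction questionnaire: "interacts with the study devices, the Vital Sync™ IM & VPMP and the BioModule".

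TM subjects are monitored by the site's usual telemetry (Protocol 10.1).

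The start rule, in Protocol 12 and again in SAP 7.10, is: "The recording of adverse events for all enrolled subjects begin after the study devices are attached".

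SAP 7.2 summarises AEs by group, severity and relationship, and adds between-group differences with 95% confidence intervals. It does not say which AE categories enter those differences. Protocol 13.3 has the same sentence, but the available text breaks off shortly afterwards, so this point rests on the SAP wording.

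**The concern.** Protocol 12.1 anticipates redness, skin burn and allergy to ECG adhesives. Telemetry is itself continuous ECG monitoring, so a mild electrode reaction can occur in either group. In SM it qualifies under category 2. In TM, if it is neither serious nor a deterioration, it fits none of the three categories on the natural reading of the term.

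If such events enter a between-group difference, the estimate mixes any true difference with a difference in what was written down. The error counts against SM. Reporting by relationship makes the device-related row visible, but TM events that were never recorded cannot be recovered from it.

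There is also a wording fault. The event that starts AE recording, attachment of the study devices, does not occur in TM on this reading.

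**Working it through.** **Text, side by side**

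| Event | SM | TM |
|---|---|---|
| SAE | collected | collected |
| Physiological-deterioration AE | collected | collected |
| Other non-serious AE linked to the group's own monitor | collected | no category; may be recorded through loose wording |
| Recording start | device attachment | not defined by the start rule |

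Some text could lead a site to record TM reactions:

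- The Synopsis speaks generally: "Subjects will be monitored for Serious Adverse Events and Device-Related Adverse Events as noted in Section 12".
- Section 8.4 does not mention group: "The BioModule will be attached to each subject and placed on the lower section of the sternum via two electrodes".
- Inclusion criterion 7 (Protocol 9.3) refers to attached study devices for all subjects.
- The relatedness item in Protocol 12.3 does not say which device is meant.
- Category 2 admits undeterminable relation.

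Note 1 in Protocol 12.2 counts comparator-related events as AEs, but it defines an AE and does not widen the list of what is collected. Hence absent or inconsistent capture, not certainly zero.

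**Group sizes**

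The documents give no AE rate or AE sample size. I use 132 per group (the LOS power figure), 140 (SAP cap) and 220 (Protocol cap). The 132 reproduces. With CV 0.65, the log-scale variance is ln(1 + 0.65²) = 0.3524. Then n = 2 × 0.3524 × (1.645 + 0.842)² / (ln 1.2)² = 131.1, rounded up to 132, at one-sided 0.05 and 80% power. The present point does not depend on it.

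**Assumptions for illustration**

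The true reaction rate r is equal in both groups (1%, 2% or 5%), TM captures none unless stated, and limits are Newcombe's (the SAP names no method). The Newcombe lower limit is L = d − √[(p₁ − l₁)² + (u₂ − p₂)²], where l₁ and u₂ are Wilson limits. All chances below are for L > 0, that is, an interval wholly against SM.

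*Reactions-only row.* With x in SM and 0 in TM at n = 132:

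- x = 4: 3.03 points (−0.35 to 7.53).
- x = 5: 3.79 points (0.23 to 8.56).

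The threshold is also 5 v 0 at n = 140 and 220. P(X ≥ 5) with X ~ Binomial(n, r):

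| n | r = 1% | r = 2% | r = 5% |
|---|---|---|---|
| 132 | 1% | 13% | 79% |
| 140 | 1% | 15% | 83% |
| 220 | 7% | 45% | 99% |

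If TM captures half of reactions, the n = 132 figures fall to 0.6%, 4% and 15%.

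*Any-AE contrast.* SAEs and deterioration AEs are collected in both groups and dilute the artefact. Let b be an assumed shared background AE rate, independent of reactions. The SM rate is 1 − (1 − b)(1 − r), the TM rate is b, and the artefact is r(1 − b). For example, b = 10% and r = 5% give 14.5% v 10%, or 4.5 points. Summing the exact binomial probabilities where L > 0:

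| n | b | r = 0 | r = 1% | r = 2% | r = 5% |
|---|---|---|---|---|---|
| 132 | 5% | 2.0% | 4% | 8% | 30% |
| 132 | 10% | 2.4% | 4% | 7% | 19% |
| 132 | 20% | 2.5% | 4% | 5% | 12% |
| 220 | 5% | 2.4% | 6% | 13% | 48% |
| 220 | 10% | 2.4% | 5% | 8% | 30% |
| 220 | 20% | 2.5% | 4% | 6% | 17% |

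**The case against.** **Focusing on the sponsor's product is a legitimate choice** in a post-market study of cleared devices. This stands as a reason for the collection rule. It does not justify an unrestricted between-group difference on events gathered under that rule.

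**The rates are assumed and may be low.** This stands. Exclusion criterion 2 (Protocol 9.4) removes patients with known allergy or sensitivity to ECG leads or similar adhesives. At a 1% rate and n = 132 the reactions-only chance is 1%.

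**Reporting by relationship already separates the device row.** This is partly true. The separation shows where the imbalance sits, but it does not make the TM count comparable.

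**No decision hangs on it.** This stands. AE differences are summarised, not tested.

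**TM does have AE collection.** This stands. Table 1 and Protocol 10.2.2 and 10.2.3 require AE checks in both phases, and Protocol 9.2 exits anyone who never starts the assigned monitoring. A reader might infer from the start rule that TM AEs go unrecorded or that SAEs are biased too. The documents do not support that: TM lacks a defined start, and no effect on any result has been shown.

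**Conclusion.** The point holds as a minor safety-reporting fault. The closed list, together with the Protocol's own use of the term study device, gives unequal capture of non-serious device reactions, and SAP 7.2 does not keep them out of the between-group differences.

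The size cannot be known from the documents. It depends on the reaction rate, the background AE rate, the degree of TM capture and the interval method, all of which are assumed here. A reader might take the 79% (n = 132) or 99% (n = 220) figure as the risk of a misleading overall AE comparison. That goes too far: those figures apply only to a reactions-only row, at a 5% rate with no TM capture. For an any-AE contrast at n = 132 the chance is about 4%, 5% to 8%, and 12% to 30% at rates of 1%, 2% and 5%. At n = 220 it is 4% to 6%, 6% to 13%, and 17% to 48%.

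The documents also do not support the inference that the whole AE comparison is invalid. The collection list treats SAEs and deterioration AEs alike in both groups, and length of stay does not depend on AE collection.

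**What to change.** **Default**

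- In SAP 7.2 and Protocol 13.3, limit between-group AE differences and their 95% CIs to SAEs and physiological-deterioration AEs.
- Report all other recorded AEs descriptively by group, without a difference, and include any TM reactions that were recorded. This stays consistent with the safety set of all participating patients (SAP 7.1.3).
- Footnote that table: collection was tied to the SM device and was not systematic in TM, so a TM count is not a rate and a zero is not evidence of none.
- In Protocol 12 and SAP 7.10, start AE recording in both groups at the later of consent and the start of the assigned monitoring. The consent limit is needed because telemetry is already ordered at pre-screening (Protocol 10.3) and could begin before consent.

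The cost is a few sentences in each document and a table footnote. The list of collected events does not change. The downside is that there is no comparative estimate of device reactions.

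**Alternative**

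Collect events related to the assigned monitoring device in both groups. This also changes Protocol 12, the relatedness item in Protocol 12.3, SAP 7.10, the AE form and site training. TM enrols and completes first, so it works only if in place before TM enrolment.
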